**Part B: CardioChek Screening for Blood tests - Cholesterol**

15B.1. Is this a fasting test?

 Yes  No

15B.2. Last meal taken (number of hours ago)

- 2 hours ago or less  
 2 to 6 hours ago  
 6 -11 hours ago  
 12 hours ago or more

15B.3. Blood lipids LDL (mmol/l)

---

15B.4. Blood lipids HDL (mmol/l)

---

15B.5. Total Cholesterol (mmol/l)

---

15B.6. LS7 Cholesterol Score

---

**Part C: CardioChek Screening for Blood tests - Blood Glucose**

15C.1. Blood Glucose (mmol/l)

\_\_\_\_\_

15C.2. LS7 Blood Glucose Score

\_\_\_\_\_

**Part D: BMI**

15D.1. Height (cms)

\_\_\_\_\_

15D.2. Weight (kgs)

\_\_\_\_\_

15C.3. BMI (Formula: Calculated BMI  
weight(kg)/height(m^2))

\_\_\_\_\_

15C.4. BMI LS7 Score (Formula: BMI < 25kg/m^2 LS7 score  
= 2, BMI 25-29.99 kg/m^2 LS7 score = 1, BMI 30+ kg/m^2  
LS7 score = 0)

\_\_\_\_\_

**Part E: Smoking**15E.1. Which of this best describes your current  
smoking status?

- Current smoker  
 Ex-smoker, quit smoking within the last 12 months  
 Never smoked, or last smoked more than 12 months  
 ago (cigarettes, ready-made or roll your own;  
 cigars cigarillos or pipe)

15E.2. If current smoker, average number of cigarettes  
smoked per day?

\_\_\_\_\_

15E.3. LS7 Smoking score

\_\_\_\_\_

**Part F: Recreational Drugs: Additional Section (Not a part of LS7 scoring)**15F.1. Smoked any of the following products in the  
past year.

- Tobacco Vapes  
 Hookah/Shisha Cannabis  
 Other recreational drugs

15F.2. If consumed recreational drugs, please  
specify.

\_\_\_\_\_

**15G.1 Alcohol: Additional Section (Not a part of LS7 scoring)**

15G.1. Have you had anything alcoholic to drink in the last 12 months?  Yes  No

15G.2. If yes, total years of alcohol consumption.

\_\_\_\_\_

15G.3. Which of the following best describes how often you CURRENTLY drink alcohol?

Less than 1 drink a day (occasional)  
 1-2 drinks a day  
 3 or more drinks a day

**Part H: Diet**

15H.1. How many portions of fresh fruit and vegetables do you eat per day on average?

\_\_\_\_\_

Note: 1 portion = 1 pc of fruit, or 1 cup of vegetables e.g., 1 apple and 1 cup of mixed salad= 2 portions.

15H.2. LS7 healthy diet component met? Tick if more than 4 portions per day  Yes  No

15H.3. How many times per week do you eat fish (100g or more) including canned or frozen fish?

\_\_\_\_\_

15H.4. LS7 healthy diet component met? Tick if more than 2 servings per week  Yes  No

15H.5. Do you add salt to your food AFTER it has been cooked?  Yes  No

15H.6. How often do you eat highly processed foods (such as sausages, ham, chips, crisps etc) and/or fast food/takeaways per week?

Never  
 Less than once per week  
 1-2 times per week  
 3+ times per week

15H.7. LS7 healthy diet component met?  Yes  No

Note: Tick if NEVER or LESS than once per week.

15H.8. During the past month, how often did you eat sweets/chocolates etc or drink fruit juices, soft drinks or energy drinks?

Never  
 Less than once per week  
 1-2 times per week  
 3+ times per week  
 (Note: Do not include diet varieties. Soft drinks are often carbonated/ fizzy and include Coca-Cola, Pepsi, lemonade, ginger beer, energy drinks (Red Bull, Lift plus), Powerade, E2, G-force. Excludes diet varieties, flavoured waters, and sports waters. )

15H. 9. LS7 healthy diet component met? Tick if less than 3 times per week  Yes  No

15H.10. How often would you have 100g of whole grains (e.g., wholegrain cereal, millet, buckwheat, rye, brown rice, quinoa, rolled oats, 3 slices of wholegrain bread, beans, dhal etc) per day?

Never  
 Less than once per week  
 1-2 times per week  
 3+ times per week

15H.11. LS7 healthy diet component met?  Yes  No

Note: Tick if less than 3 times per week

15H.12. LS7 Healthy Diet score

if 4 to 5 components are ticked.  
 if 2 to 3 components are ticked  
 if 0-1 components are ticked

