## ASSESSMENT INFORMATION

The Primary Outcome measure of **blood pressure** will be collected as part of the LS7 questionnaire. The LS7 is a simple scoring system to assess cardiovascular health with scores ranging from 0 to 14, with the overall LS7 score categorised as inadequate (0–4), average (5–9), or optimum (10–14) cardiovascular health. These are; blood pressure, cholesterol, glucose, body mass index, smoking, physical activity, and diet.[37] The total LS7 score as well as individual LS7 items apart from blood pressure are secondary outcomes.

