## The Life's Simple 7 scale

Table 3. Definitions of the LS7 categories \*

Life's Simple 7	Level of Cardiovascular Health		
	Poor	Intermediate	Ideal
Lifestyle Factors			
Body mass index, kg/m 	≥30	25.0–29.9	<25
Physical activity, min/day	0 MVPA	>0 – <150 MPA or MVPA >0 to <75 VPA	≥150 MPA or MVPA ≥75 VPA
Healthy diet score	0–1 components	2–3 components	4–5 components
Cigarette smoking	Current	Quit <12 months ago	Never or quit >12 mo
Medical risk factors			
Blood pressure, mmHg	≥140/≥80	120 – 139/80–89 or <120/<90 with med	<120/<80 no med
Total cholesterol, mg/dL	≥240	200–239 or <200 with medication	<200
Fasting blood glucose, mg/dL	≥126	100–125	<100
Glycosylated Hemoglobin, %	≥6.5 or taking diabetes med	5.7–6.4	<5.7

M, moderate; V, vigorous; PA, physical activity.

(i) Fruits and vegetables ≥4.5 cups/day; (ii) Fish 3.5-oz servings (preferably oily fish) ≥2 servings/week; (iii) Sodium <1500 mg/day; (iv) Sweets/sugar-sweetened beverages ≤450 kcal (36 oz)/week; (v) Whole grains (1.1 g of fiber in 10 g of carbohydrates), 1-oz-equivalent servings ≥3 servings/day.

\*Note: Fasting blood glucose in mmol/l is ≥7.00 (poor), 5.55–6.99 (adequate) and <5.55 (optimum). Plasma total cholesterol, mmol/l ≥ 6.22 (poor), 5.18–6.21 (adequate) < 5.18 (optimum).

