## 31. SECONDARY END POINTS

Secondary outcomes include: (1) difference in the mean change in the LS7 scale score at 6 months post-randomisation between UC and HWC (2) the change in individual lifestyle components of the LS7 scale (BMI, smoking, physical activity, and diet) at 6 and 12 months; (3) diastolic BP (mmHg); (4) quality of life (EQ-5D-5L), (5) awareness of stroke risk factors and warning signs, (6) medication adherence (7) cognitive outcomes (8) adverse events including hospitalisations; and (9) health service use and costs.

The LS7 scale includes BP, cholesterol, blood glucose, BMI, smoking, physical activity, and diet. The score of LS7 will be calculated by providing 2 points for ideal, 1 point for intermediate, and 0

points for poor status of each of the 7 individual factors. Ideal levels of health factors were: non-smoker or quit >1 year ago; BMI <25 kg/m^2; BP <120/80 mm Hg; total cholesterol <200 mg/dL; fasting blood glucose <100 mg/dL; ≥150 min/week of physical activity; and a healthy diet score (≥4 components). Study participants who were treated to target levels for hypercholesterolemia, hypertension, or diabetes mellitus were classified as intermediate for the respective health factor. Thus, the LS7 summary score will range from 0 to a maximum of 14 points, with a higher score indicating healthier status.

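### Forms B and F credit the LS7 fish component only above two servings a week, but Table 3 defines it as met at two or more

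*Protocol*

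**What the plan says.** The note under Table 3 (The Life's Simple 7 scale) lists five healthy diet components. The second is "Fish 3.5-oz servings (preferably oily fish) ≥2 servings/week".

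Appendix C turns this into form items in Section 15, Part H, worded identically on Form B (baseline) and Form F (follow-up). Item 15H.3 asks how many times per week the participant eats fish, in amounts of 100 g or more, and leaves a blank for the answer. Item 15H.4 then gives the scoring rule: "LS7 healthy diet component met? Tick if more than 2 servings per week".

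Item 15H.12 converts the number of ticked components into the diet score. The top category applies "if 4 to 5 components are ticked", the middle at 2 to 3 and the bottom at 0 to 1. Section 31 (Secondary end points) says: "The score of LS7 will be calculated by providing 2 points for ideal, 1 point for intermediate, and 0" points for poor. On the status of these scores, the Assessment Information section says: "The total LS7 score as well as individual LS7 items apart from blood pressure are secondary outcomes".

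**The concern.** The definition and the form disagree about one value, exactly two servings a week. That value is the target itself, so it is one a coached participant may well reach.

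Two kinds of change are misread. A participant who moves from one fish meal a week to two has reached the defined target, but the form records the component as still unmet. A participant who moves from two to three already met the definition at the start, but the form records a newly met component. Diet is one of seven LS7 domains and is scored only 0, 1 or 2, so one wrong component can move the domain, and the LS7 total, by a full point.

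Section 31 lists the LS7 score change first among the secondary outcomes and names diet at 6 and 12 months. Section 11 (Secondary aims) adds 3 and 9 months for the individual LS7 behavioural factors.

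**Working it through.** The plan states no figure to reproduce here. The check compares the two rules and then traces the effect through the score.

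**1. Where the rules differ.**

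| Fish, servings per week | Table 3 note (≥2) | Item 15H.4 (>2) |
|---|---|---|
| below 2 | not met | not met |
| exactly 2 | met | not met |
| above 2 | met | met |

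They differ at exactly 2 and nowhere else, whether 15H.3 is filled in with whole numbers or fractions. Serving size does not explain the gap: 3.5 oz is about 99 g, and 15H.3 asks about 100 g or more.

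**2. Effect on the diet score for someone at exactly 2.** Let k be the number of the other four components met. The definition gives k + 1 components and the form gives k. The score is 0 for 0–1 components, 1 for 2–3 and 2 for 4–5.

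| k | Patterns of the other four | Score by definition | Score by form |
|---|---|---|---|
| 0 | 1 | 0 | 0 |
| 1 | 4 | 1 | 0 |
| 2 | 6 | 1 | 1 |
| 3 | 4 | 2 | 1 |
| 4 | 1 | 2 | 2 |

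The form is one point too low at k = 1 and k = 3, which is 4 + 4 = 8 of the 16 patterns. These are counts of patterns, not of participants.

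**3. Share of participants affected.** The protocol gives no diet distribution, so both inputs are assumptions:

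- s, the share of participants at exactly 2 servings;
- p, the probability that each of the other four components is met, taken as equal and independent, and with those components scored correctly.

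With q = 1 − p:

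P(k = 1 or k = 3) = 4pq³ + 4p³q = 4pq(p² + q²)

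- p = 0.1: 4 × 0.1 × 0.9 × (0.01 + 0.81) = 0.295
- p = 0.2: 4 × 0.2 × 0.8 × (0.04 + 0.64) = 0.435
- p = 0.5: 4 × 0.5 × 0.5 × (0.25 + 0.25) = 0.500

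The expression is symmetric about p = 0.5, where it is largest. Multiplying by s gives the share of diet scores that are one point too low:

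| s | p = 0.1 | p = 0.2 | p = 0.5 |
|---|---|---|---|
| 10% | 3.0% | 4.4% | 5.0% |
| 20% | 5.9% | 8.7% | 10.0% |
| 30% | 8.9% | 13.1% | 15.0% |

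At s = 20% this is about 6% to 10% of diet scores at a visit, or roughly 21 to 36 of the 360 planned participants (0.059 × 360 = 21; 0.10 × 360 = 36).

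**The case against.** The best reply is that this is small and recoverable. The primary endpoint is systolic blood pressure, so the primary analysis and the sample size are untouched. Diet is one domain of a secondary score. The same wording is used in both arms and at every visit, and the raw frequency is kept in 15H.3, so a statistical analysis plan could derive the component correctly without the tick box. All of that stands, and it limits the importance of the point. It does not remove the conflict: the protocol prints two rules, and anyone who follows the form scores against the protocol's own definition. Identical wording makes the error cancel for a participant who stays at two servings only if the rest of the diet also stays put. It does not cancel for someone who moves to or from two.

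A reader might infer three stronger things, and the document supports none of them.

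- **That diet scores are wrong in general.** Only participants at exactly two servings are affected by this rule, and among those only when one or three other components are met.
- **That the comparison between arms is biased by a known amount or in a known direction.** This would depend on how many participants in each arm move to or from exactly two servings, which the protocol does not give. The percentages above concern scores at a visit, not a treatment effect.
- **That the sodium component is also misscored.** Table 3 gives "Sodium <1500 mg/day", and item 15H.5 asks "Do you add salt to your food AFTER it has been cooked", yet the only tick rule that follows is "Note: Tick if NEVER or LESS than once per week". That rule fits the processed-food frequency in 15H.6 and not a yes/no answer, so as printed the added-salt answer enters no score. This is not a contradiction. No item on the form measures milligrams per day, so any scoring is a proxy, and the protocol nowhere says that 15H.5 must count or how it would combine with 15H.6. A rule that combined the two would be a preference between proxies, with no source in the document. What can fairly be asked is that the sponsor state whether 15H.5 is meant to enter the sodium component, since unlike the alcohol and drug items it is not labelled as outside LS7 scoring.

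**Conclusion.** The concern holds for the fish component. Table 3 and item 15H.4 contradict each other on Forms B and F, and a participant at exactly two servings a week is denied a component that the protocol's definition grants. The result is a diet score, and hence an LS7 total, one point too low in 8 of 16 patterns of the other components.

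The share of participants affected cannot be known from the protocol. The range of about 6% to 10% rests on an assumed 20% at exactly two servings and on equal, independent probabilities of 0.1 to 0.5 for the other four components; 10% is the most that this model gives at that share. The consequence is confined to secondary outcomes and can be fully corrected wherever 15H.3 was completed.

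**What to change.** - On Form B and Form F, reword 15H.4 so that the component is ticked at two or more servings per week, in line with the Table 3 note.
- For every visit at which Part H was completed, recompute 15H.4 and 15H.12 from the number in 15H.3, and recompute the LS7 total wherever one is scored, so that records already collected follow the same rule.
- Do this in one pass with the rest of Part H. Item 15H.11 credits whole grains for eating them fewer than three times a week, whereas Table 3 requires at least three servings a day. If that is left reversed, the recomputed diet score will still be wrong.
- Add one sentence saying whether 15H.5 is intended to enter the sodium component.

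The fish correction costs one wording change on each of two forms and a short rescoring from data already held. It needs no new data collection, except that a visit with 15H.4 filled in as not met and 15H.3 left blank cannot be rescored.

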### Part I: Physical activity

15I.1. How often do you perform moderate to vigorous physical activity for at least 10 minutes that makes you breathe harder/break into a sweat?

4 times a week or more  
 1-3 times a week  
 Never

15I.1.1. How many hours per week would you spend performing these physical activities?

Less than 2.5 hours per week  
 2.5 hours per week or more

15I.2. LS7 Activity score

\_\_\_\_\_

15J. Total LS7

\_\_\_\_\_

Note: Score out of 14.

### Section 16: Stroke risk by the Stroke Riskometer App

16.1. Risk assessment date

\_\_\_\_\_

16.2. Riskometer assessment done by  CRA  HWC  Participant

16.3. Father or mother had a stroke or heart attack before reaching the age of 65.

Yes  No  Unknown

16.4. 5- year Stroke risk (%)

\_\_\_\_\_

16.5. 5- year Relative risk (%)

\_\_\_\_\_

16.6. 10- year Stroke risk (%)

\_\_\_\_\_

16.7. 10- year Relative risk (%)

\_\_\_\_\_

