### 11. SECONDARY AIMS

The **secondary aims** are to determine the effectiveness of HWC in improving

1. Overall cardiovascular disease (including stroke) risk at 6 months post-randomisation based on the LS7 compared to Baseline

2. Individual LS7 behavioural risk factors at 3-, 6- 9- and 12- months post-randomisation compared to Baseline
3. Awareness about stroke symptoms, risk factors and their management 6- and 12- months post-randomisation compared to Baseline
4. Quality of life, at 6- and 12- months post-randomisation compared to Baseline
5. Cognitive outcomes at 6-, and 12- months post-randomisation compared to Baseline
6. Mood outcomes compared to Baseline
7. Adherence to CVD medications at 3, 6-, and 9 and 12- months compared to Baseline
8. CVD/adverse outcomes at 12 months post randomisation.
9. Health and service costs at 12 months post randomisation
10. Productivity status at 12 months post randomisation

Secondary outcomes are:

1. systolic blood pressure, total cholesterol, blood glucose at 6-months post randomisation
2. change in proportion of participants in 'high' and 'intermediate' to 'low' risk on LS7 at 6-months post randomisation
3. Stroke risk from Stroke Riskometer – 5- year absolute and relative risk at 6- and 12-months post randomisation
4. Quality of life (EQ5D) at 6-months post randomisation
5. Stroke awareness at 6- and 12-months post randomisation
6. Cognitive assessment score (Montreal Cognitive Assessment)
7. Medication adherence (Self-Efficacy For Appropriate Medication Use Scale (SEAMS))
8. CVD adverse outcomes (fatal and nonfatal stroke, TIA, myocardial infarction and heart failure, death attributable to CVD and all-cause mortality)
9. Healthcare and community service costs assessed as self-reported service use questionnaire at follow up. Productivity status will be self-reported and will include items regarding status (e.g., paid work, voluntary work, homemaker, student, unemployed), hours (e.g., full/part time), compared to hospitalisation pre-stroke status.

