### 3.5 CASE RECORD FORMS AND QUESTIONNAIRES

#### 20. LIST OF QUESTIONNAIRES

Table 1. List of outcome measures

Outcome measure	Baseline	3	6	12
Demographic Factors: Age, sex, ethnicity, employment, education, marital status	✓			
Event type - stroke and pathological subtypes, or TIA and event date (physician diagnosed)	✓			
Hospitalization details: hospital, date of admission, date of discharge	✓			
Event details (revascularization and planned procedures) from medical records	✓			
Hospital Anxiety and Depression Scale	✓	✓	✓	✓
Stroke awareness (recognition of risk factors, knowledge of actions) [61]	✓	✓	✓	✓
Quality of life (EQ-5D-5L) [62]	✓		✓	
Cognitive functioning by MoCA [63]	✓		✓	
Medication adherence and self-efficacy (SEAMS) REF)	✓	✓	✓	✓
Physical measurements (non-fasting blood test, SBP/DBP, BMI, HR)*	✓		✓	
Absolute and relative 5-year risk of stroke (as measured by Stroke Riskometer app)	✓		✓	
Lifestyle factors (Diet score, physical activity, smoking, alcohol)	✓	✓	✓	✓
CVD outcomes, recurrent events, hospitalisation (stroke, CVD events) self-report and/or from clinical records	✓	✓	✓	✓
Health and Service costs: NMDS (NZ)			✓	✓
Productivity level NMDS (NZ)	✓	✓	✓	✓
Participant feedback questionnaire – Intervention group only	✓	✓	✓	✓

Items will include demographic factors, medical history, lifestyle risk factors, awareness of stroke risk factors, warning signs, symptoms and actions;[64] depression screening test (Hospital Anxiety and Depression Scale) health related quality of life ([EQ-5D-5L](#)),[62] health-care resource

use questionnaire, cognitive assessment (Montreal Cognitive Assessment MoCA) and participant satisfaction questionnaires. See 2 for details of measures collected at each timepoint. Life's Simple 7 score will be calculated from corresponding measurements of smoking, BMI, physical activity, healthy diet score, blood total cholesterol, glucose level and BP.[37]

Table 2. Life's Simple 7

Modifiable factors	Poor health	Intermediate health	Ideal health
Smoking status	Current smoker	Former ≤ 12 months	Never or quit > 12 months
Body mass index	≥ 30 kg/m 	25–29.9 kg/m 	< 25 kg/m 
Physical activity	No physical activity	1–3 times, less than 2.5 hours per week	≥ 4 times per week, 2.5 hours or more
Healthy diet score	0–1 component	2–3 components	4–5 components
Total cholesterol	≥ 240 mg/dL	200–239 mg/dL or treated to goal	< 200 mg/dL

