### **Stroke Riskometer stroke risk assessment**

The validated Stroke Riskometer is a mobile application that is free to download from App stores. The Stroke Riskometer App [80] is a novel, evidence-based app for the primary prevention of stroke. The App incorporates several evidence-based tools to promote behaviour change aligned with internationally recognised stroke prevention guidelines.[81] These include:

- Provision of feedback on *absolute* risk of stroke within the next 5 to 10 years *and* compares a person's *relative* risk with those of a person of the same age and sex without risk. This approach has been demonstrated to motivate behaviour change when used in conjunction with other methods.[82]
- Employs *tailored self-management* strategies including goal setting to engage the person in behaviour modification
- Includes *information on stroke risk factors and warning signs* aligned with the internationally relevant Face, Arm, Speech, Time (FAST) international mass media campaign.
- Uses *reminders*, known as “push notifications”, to prompt users to achieve their goals. Such reminders have been shown to increase adherence to programs.[83]

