Data from the ARCOS V study on stroke risk factor prevalence and significance by age, sex and ethnicity, life satisfaction and other measures will guide the emphasis of the intervention on which particular health behaviours to focus on. As such, providing/referring to educational material is relevant to this model, including information booklets from the Heart and Stroke Foundation (<https://www.heartfoundation.org.nz/resources>) which include recommendations and guidelines on duration and frequency of exercise, weight loss, healthy eating, smoking cessation, and reducing alcohol intake,[88] and information about the free Stroke Riskometer mobile app (for stroke awareness and risk assessment, <https://nisan.aut.ac.nz/Stroke-Riskometer>). This is also in line with recent evidence recommending that RCT's for secondary disease prevention in TIA/minor stroke should include a combination of educational and behavioural interventions.[89-91]

---

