### DATA COLLECTION AND FOLLOW-UP

Research assistants (RAs) will be provided training and ongoing supervision to conduct assessments. All assessments will be conducted in a standardised manner in accordance the Protocol. The Project Manager will conduct the randomisation and assign cases to the RAs. RAs will be blinded to the treatment group.

---

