### 32. POWER CALCULATION

The sample of 360 participants will provide a simulated 90% statistical power (two sided  $\alpha=0.05$ ,  $\beta=0.10$ ) to detect a clinically significant 6 mmHg (SD $\pm$ 20) difference in systolic blood pressure change at 6 months post-randomisation, assuming 20% non-compliance/loss to follow-up.

Based on our RIBURST data (a observational stroke risk study)[94] data in NZ general population (n=1265, with 0.07% incident stroke or TIA), the required sample size (n=360) will also provide 90% power (2-sided alpha) to detect 20% relative risk reduction in 5-year absolute risk of stroke. The estimated 5-year risk of stroke after TIA and minor stroke in NZ appeared to be greater than that in Europe,[4] likely due to greater risk of stroke in Māori and Pacific people constituting 20% of the NZ RIBURST Study population.

---

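### Form F lets the unblinded coach or the participant complete the follow-up Stroke Riskometer score, so the assessor of a listed secondary outcome can differ by arm

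*Protocol*

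**What the plan says.** Section 11 (Secondary aims) lists the Stroke Riskometer 5-year risk among the secondary outcomes: "absolute and relative risk at 6- and 12-months post randomisation". Table 1 in Section 20 gives the same outcome as "Absolute and relative 5-year risk of stroke (as measured by Stroke Riskometer app", ticked at baseline and 6 months only.

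Appendix C, Form F, is the single follow-up form for the 3-, 6-, 9- and 12-month assessments. Its Section 16 records who produced the score: "16.2. Riskometer assessment done by", with boxes for CRA, HWC and participant. Nothing on the form limits that choice by arm or by visit.

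The Trial Design section calls the trial open-label with single-blinded end-points. Under Data Collection and Follow-up, "RAs will be blinded to the treatment group". The visit reminder sheet in Appendix A likewise protects only the research assistants, and the Randomisation Procedure hides the randomisation form from them. Usual-care participants are told their group (Usual Care), and only the HWC arm has a coach (Section 27).

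**The concern.** Blinded end-point assessment protects a comparison only if the same kind of assessor, without knowledge of the arm, scores both groups. Item 16.2 allows two kinds of assessor who are not covered by the blinding. One of them, the coach, can exist in one arm only. If some intervention scores come from coaches and all usual-care scores come from CRAs or participants, assessor and arm are partly confounded, and no analysis can separate them afterwards.

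Two things are at stake. The first is the between-arm comparison of 5-year risk. It may carry further, because the Health Economic Evaluation names the change in absolute 5-year stroke risk as one possible basis for modelling strokes averted. The second is the blinding itself. Research assistants capture data in REDCap and complete Form F. A tick against HWC reveals the allocation on a form they work with, although the randomisation form is hidden from them for exactly that reason.

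**Working it through.** **Passages set side by side**

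| Question | Where | Answer |
|---|---|---|
| Is the Riskometer score an outcome? | Section 11; Table 1 | Yes, secondary |
| Who may complete it at follow-up? | Form F, 16.2 | CRA, HWC or participant |
| Who is blinded? | Data Collection and Follow-up; Appendix A | Research assistants only |
| Who has a coach? | Section 27 | HWC arm only |
| Are coach or participant scores excluded from the outcome? | Nowhere stated | No rule |
| When is it assessed? | Section 11 | 6 and 12 months |
| | Table 1 | Baseline and 6 months |

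The abbreviation HWC elsewhere means the intervention or its arm. In a field naming who did the assessment, only the coach makes sense. It follows that the assessor can depend on the arm.

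The two timing entries also disagree. The 12-month assessment is by telephone only (Section 29), and Table 1 schedules no physical measurements then. How a 12-month score would be produced, and by whom, is therefore open.

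**The plan's nearest figure.** Section 32 claims 90% power with n=360 "to detect 20% relative risk reduction in 5-year absolute risk of stroke". It cannot be reproduced, because no mean or SD of the risk score is given.

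- Read as events at the quoted 0.07%: p1 = 0.0007, p2 = 0.8 × 0.0007 = 0.00056, 180 per arm. SE = √[(0.0007 × 0.9993 + 0.00056 × 0.99944)/180] = 0.00264. Power = Φ(0.00014/0.00264 − 1.96), about 3%.
- Read as a continuous score: 90% power for a 20% difference needs a coefficient of variation (CV) of at most 0.20/[(1.96 + 1.2816) × √(2/n)]. That is 0.585 with n = 180 per arm, and 0.524 with n = 180 × 0.8 = 144 per arm after 20% loss.

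The point here does not depend on that claim. The second reading only supplies a CV for the illustration.

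**Illustration of assessor bias (share, shift and CV are assumptions).** Suppose there is no true effect and 144 per arm are analysed. A share f of the HWC arm is scored by a different kind of assessor, whose scores are shifted by a relative amount b. The apparent relative difference is d = f × b, with SE = CV × √(2/144). The two-sided rejection rate is Φ(d/SE − 1.96) + Φ(−d/SE − 1.96). It is the same for an upward or a downward shift.

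Worked case: CV 0.52, f = 0.5, b = 0.10. Then d = 0.05, SE = 0.52 × 0.1179 = 0.0613 and d/SE = 0.816. The rate is Φ(−1.144) + Φ(−2.776) = 0.129.

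| f | b | d | Rate at CV 0.52 | Rate at CV 0.8 |
|---|---|---|---|---|
| 0.25 | 10% | 2.5% | 6.9% | 5.8% |
| 0.5 | 10% | 5% | 12.9% | 8.3% |
| 1 | 10% | 10% | 37.2% | 18.5% |

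The nominal rate is 5%. A small shift in a minority of scores does little. A shift across most of the arm does a great deal.

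**The case against.** **The form may be a carry-over.** Item 16.2 is a record of who did the assessment, and no procedure assigns the Riskometer to a coach. The body text gives assessments and data capture to research assistants, and neither the session outline nor the coach's form (Form Z) has a Riskometer step. The same three options stand on Form B, completed before randomisation, when no participant has a trial coach. Form F also keeps other baseline-only text, such as the stop for systolic pressure below 130. All of this stands. It makes routine coach scoring unlikely, but it does not close the option, and no rule keeps such scores out of the outcome.

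**Affected scores could be found later.** Because the assessor is recorded, coach-completed scores can be identified. That also stands. Dropping them afterwards, however, would create missing values in one arm only.

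**Other secondary outcomes are self-reported by unblinded participants.** True, so participant completion alone does not set this outcome apart. Possible scoring by a coach, who exists in one arm only, does.

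**Stronger readings that a reader might infer, and that the documents do not support:**

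- *That self-completion in usual care dilutes the primary blood-pressure contrast.* Section 24 has coaches provide "information about the free Stroke Riskometer mobile app", and of the app's risk feedback the protocol says "This approach has been demonstrated to motivate behaviour change when used in conjunction with other methods". But the only scheduled follow-up use up to the primary endpoint is at 6 months, where Form F places blood pressure (Section 15A) before the Riskometer (Section 16). Use at 12 months comes later, and baseline use precedes randomisation in both arms.
- *That the app is a required part of the intervention.* It enters only as information or referral.
- *That this outcome has its own stated power.* The sentence in Section 32 does not name the Riskometer. The link runs through the outcome definition and the cited app paper.
- *That the bias favours HWC, through particular inputs.* The protocol does not list the app's inputs, and nothing in it fixes a direction.

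**Conclusion.** The concern holds in a limited form. Form F permits, without requiring, unblinded and arm-dependent scoring of a listed secondary outcome. That conflicts with the stated blinded end-point design, and a visible HWC tick could disclose the allocation to a research assistant. The conclusion rests on reading HWC in item 16.2 as the coach, and on the absence of any rule excluding such scores.

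The size and direction of any bias cannot be derived from the protocol. Under the assumed values above, the false-positive rate runs from about 6% to 37%, depending mainly on how many scores are affected. The effect of the app on the primary systolic contrast is not in question. The change is worth making because it is nearly free and removes the problem entirely.

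**What to change.** 1. On Form F, remove the HWC and Participant options from item 16.2. State in the protocol that the blinded CRA computes the outcome score in the same way for both arms, on a study device.
2. If coach or participant scores are wanted for other purposes, record them on a form that research assistants cannot see and exclude them from the outcome. The CRA should still produce a score for every assessed participant, so that exclusion does not leave gaps in one arm only.
3. Reconcile the timing: Section 11 has 6 and 12 months, while Table 1 has baseline and 6 months. If 12 months is kept, say how the blinded CRA obtains the score at a telephone assessment.

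The cost is a form edit, a sentence or two in the protocol, and a few minutes of CRA time per visit. Since the protocol does not list what the app needs as input, the team should confirm that the CRA has it at each retained time point.
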